17.7. Process evaluation: data analysis

Data analysis will be on-going and iterative throughout the study. Interviews, focus groups and recruitment discussions will, with consent, be audio-recorded, transcribed verbatim and edited to ensure anonymity of respondent. Contemporaneous field notes from non-participant observation will be anonymised as they are produced to ensure anonymity of participants. The analysis will be theoretically-informed by our theoretical frameworks (44-46) and conducted according to the standard procedures of rigorous qualitative analysis(52) including open and focused coding, constant comparison, memoing,(53) deviant case analysis,(54) and mapping.(55) We will undertake independent coding and cross checking. Data will be analysed collectively in weekly 'data workshops' where the qualitative research team share and exchange interpretations of key issues emerging from the data, as well as workshops with the broader research team and PPI group.

17.8. Process evaluation data handling

The process evaluation will fully comply with the terms of the General Data Protection Regulation (GDPR) and Data Protection Act 2018.

To support anonymity of the participants, all clusters will be anonymised and given a unique reference number that will be used throughout all notes, transcriptions and publications. Identifiable data (e.g. contact details) will be held on a separate database (i.e. will not be linked to any data) and will only be used to contact the participant about the study.

For interviews, focus groups and audio-discussions when participants have been recruited into the study and given informed consent, they will be assigned a non-identifiable reference number and all data (paper and electronic) will use this number. Interviews, focus groups and recruitment discussions will be digitally recorded and transcribed verbatim in order to ensure fidelity to the views and actions of participants is retained in the analysis. Throughout transcription any identifiable information shall be anonymised. In the event that any participant was to withdraw their consent, any of their existing data would be destroyed and would not be used in further analysis.

Transcription of interviews and focus groups will be done by a professional company external to the research team.

Brief written feedback will be assigned a non-identifiable reference number and all data (paper and electronic) will use this number. We do not expect any special category or identifiable data will be collected or recorded regarding staff (or parents) in this written feedback. Any identifiable information shall be anonymised.

In relation to non-participant observation research no special category or identifiable data will be collected or recorded regarding parents or staff. Staff job roles will be recorded and included in the fieldnotes as this information is central to the core aims of the study. During non-participant observations no personal identifiable information will be recorded or any participant details, ensuring participant anonymity.

All data will be held on secure, password-protected Northumbria University servers. The analysis will be undertaken by the process evaluation researchers and they will be the only members of the team who will have access to field notes, audio-recordings and anonymised interview transcripts. The analysis will take place on Northumbria University computers. The digital voice recordings will be destroyed at the end of the study. All other records will be retained in a secure archive setting for 10 years to facilitate future analysis and publication of the study material.

17.9. Ethical issues related to the process evaluation

While every precaution will be taken to preserve patient anonymity and confidentiality there will be limits to this. In the event that the researcher has concerns for the well-being of a participant or others, action would be taken to disclose concerns to a named contact (e.g. the participant's GP) though the researcher would speak to the participant about this first. If a participant were to disclose anything indicating unsafe practices or misconduct, they would be directed to follow the complaints procedures (in PIL).

17.10. Relationship between process evaluation and main trial

The process evaluation team will present anonymised emerging findings to the trial team, PMG, TSC and PPIE stakeholders on the potential determinants of trial set-up and recruitment. These might include cluster-specific issues, issues across multiple clusters, or at the level of the organisation of the trial. We will work with the TMG, CHaRT and PPIE stakeholders, and where appropriate specific clusters, to develop a plan of action. We will focus on aspects that are

amenable to change. On-going cluster feedback will be undertaken in conjunction with CHaRT and TSC. All feedback to trialists and clusters will be supportive and constructive.

18. Trial sample size and proposed recruitment rate

18.1. Sample size

CHESS is designed to detect a target difference of 2 points on the PEDI-CAT ADL: for 90% power and 2-sided 5% α , assuming a 5-point SD from our cohort study of similar children, we require a sample size of 266 ignoring the clustered design. There is no minimally important difference established for the PEDI-CAT ADL. From our pilot data children improve about 8 points over a 24-month period, adding 2 points to that trajectory improves PEDI-CAT ADL scores by about 6 months crudely speaking -- with the caveat that improvement is not linear. A 2-point difference is equivalent to a moderate standardised mean different of 0.4, which is a worthwhile and achievable difference given the lack of an effective intervention for these children.

The unit of randomisation is at the service level. Inflating for the clustered design assuming an ICC of 0.1 (from our cohort study) and 40 clusters of size 20 has 90% power. Based on our previous studies in this population, we have assumed a drop-out of about 15%, each cluster will recruit 24 children, a total sample size of 960.

18.2. Recruitment rates

To optimise the timing and process of recruitment, we will sample and recruit all 24 children per cluster in a single sweep, by sampling across the cluster caseload (current cases and waiting list), inviting children and parents to participate, and collecting baseline data from those consented.

Our pre-trial work⁴⁶ showed that a cluster RCT is acceptable to therapists, and preference for treatment allocation at cluster-level has continues to be emphasised by potential clusters. Cluster sizes are likely to vary from small (~5 therapists) to large (>70 therapists), with an average of around 16 therapists. The overall caseload sizes per cluster also vary, from <100 to >7000 children (0-21yrs), averaging around 1088. There is no published, conclusive data on the breakdown of these caseloads; based on our scoping and previous work, we estimate around a third to be preschool age, of whom at least half with difficulties in self-care.

Our projection is based upon 40 clusters contributing 24 participants each over 3 months. Incorporating a staggered cluster set-up, we would expect to recruit the first 240 participants by month 16 (i.e., after 6 months' recruitment), 720 children and parents by month 22 and the remaining 240 by month 28, making a total of 960 participants after 18 months of recruitment.

Figure 2: Recruitment projection

18.3. Internal pilot study

We plan an internal pilot phase to test recruitment and randomisation over the first 9 months of recruitment (month 11 – month 19). Recruitment of 60% of the anticipated number of randomised clusters and participants at month 19 will be used to inform progression from pilot phase to full trial.

Table 4: Stop/go criteria at 9 months

| | Red | Amber | Green |
|---|--|---|--|
| Cluster recruitment | <60% (<14 clusters) | 60-100% (≥14 clusters) | 100% (24 clusters) |
| Participant recruitment | <60% (<288 pts) | 60-100% (≥288 pts) | 100% (480 pts) |
| Intervention and trial process, including recruitment, acceptability | Qualitative work is strongly suggestive that one or both of the intervention and trial delivery are unacceptable with substantial change | Qualitative work suggests that one or both of the intervention and trial delivery require change. These changes are possible but some are non-trivial. | Qualitative work does not suggest problems with the intervention or trial delivery |
| Action | Discuss urgently with the TSC and potentially the funder, considering all options including discontinuation. | Consider recruitment strategies and blockages (if centres are not open), including trouble shooting, revised training and support, open additional centres | Proceed seamlessly whilst considering recruitment strategies |

19. Project timetable and milestones

Start date: 1 Feb 2024. Duration: 48 months. Milestones: prefunding: regulatory approvals, cluster engagement; months 1-6: study tailoring with PPIE, set-up, authorisations; months 1-26: recruitment and training of clusters; month 11-16: internal pilot; month 11-28: child and parent recruitment; month 17 to 40: follow-up to 12 months after intervention; months 41-48: analysis, interpretation, reporting and start of dissemination (Figure 3).

Figure 3: Gantt chart

20. Statistical analysis

A comprehensive economic evaluation will be conducted, including a within trial analysis, modelbased analysis, discrete choice experiment and budget impact analysis. We will also conduct a Study Within a Trial (SWAT). The main outcome for both the within trial and the model-based analyses will be a cost-consequence analysis (CCA), in which a range of outcomes are presented to allow readers to form their opinion on the relevance and relative importance to their decisionmaking context. The purpose of the CCA is twofold: (i) to allow us to present impacts to the child and carer that under current methods cannot be aggregated together and (ii) identify and report outcomes that are not reflected in health related QALY estimates. Full details of the health economics analyses will be documented in the Health Economics Analysis Plan (HEAP).

21.1. Within-trial economic evaluation

The cost perspective (i.e. whose costs are considered) for all analyses will be health, social care and the family, with a narrower perspective of health and social care only being included as part of a sensitivity analysis. The perspective for effects will be child and carer, with a narrower perspective of child only or carer considered in sensitivity analyses. All costs associated with the delivery of the intervention will be collected as part of a micro-costing exercise at individual study centres. Centre level data will be supplemented with participant level data collected using study CRFs. The use of health and care services, including out of pocket expenses will be collected using a participant service use questionnaire (SUQ) administered at baseline, 6 months and 12 months post randomisation. The SUQ will be developed from our item bank of previous questionnaires and other relevant data collection tools (www.dirum.org). Time and travel costs borne by child and carers in accessing and using services will be estimated using information from the SUQ and from the responses to a one-off time and travel questionnaire (TTQ) administered at 9 months post randomisation. The TTQ will be developed from those used successfully in previous NIHR funded studies. Both the SUQ and the TTQ will be developed in partnership with the study PPIE group. The unit costs of NHS and PSS resource use will be estimated from study specific estimates and routine data sources.^{49, 50} Unit costs will be combined with information on the use of services to estimate a cost for each participant/carer. For child/carer costs, the time and travel costs of accessing care will be estimated using the responses to the TTQ and data on the use of services. To this will be added the monetary cost of any private health care.

Health Related Quality of Life (HRQoL) will be calculated using a variety of measures. For the child, HRQoL will be measured using the proxy version of the CHU-9D.⁴¹ This is currently validated for children ≥5-years-old, however a proxy version with additional guidance is available for children under 5. Recent evidence from Australia⁴¹ concluded that the measure was found to be valid and reliable to measure HRQoL in children aged 2–4 years. As there is currently no evidence on the validity and reliability of the proxy CHU-9D for children under 2, we will conduct a sensitivity analysis which excludes those children aged under 2 at baseline from the analysis sample. For the parent carers, HRQoL will be measured using the SF-36v2. To further assess the parent carer's care-related quality of life, ICECAP Carer Experience Scale (CES) will also be collected. This tool focuses on 'care-related quality of life' rather than health-related quality of life, comprising attributes that are pertinent to unpaid carers.

In the base case analysis QALYs will be based on responses to the CHU9D (child) and the SF-6D, derived from response to the SF-36 (parent carer). QALYs for each participant will be obtained by scoring responses to the two tools at baseline, 6, 12 months post randomisation using scoring systems available at the time of analysis that are appropriate to each tool. QALYs cannot be calculated for the CES. The mean CES index at each data collection point will be estimated, with this information used to complement the QALYs calculated from the SF-6D in the CCA.

An appropriate regression model will be fitted to estimate marginal costs and QALY gains; controlling for baseline covariates. Data will be presented as point estimates and bootstrapping techniques will be used to characterise imprecision (Barber 2000). The incremental costs and QALYs based on the CHU9D and SF-6D will be reported in a CCA, presented in the form of a balance sheet. Also included in the CCA will be the mean responses to the CES, and other outcomes from the trial that cannot be directly mapped back on to the CHU9D, SF-6D, the CES or costs. The results will be expressed in the form of incremental costs, incremental QALYs and incremental cost-per-QALY. Stochastic sensitivity analysis will utilise the non-parametric bootstrapping technique with multiple bootstraps to explore the impact of statistical imprecision surrounding the point estimates of costs, QALYs (and other outcomes as appropriated in the CCA) and incremental cost per QALY. For the CCA and cost per QALY analysis, the cost-effectiveness (CE) plane will be used to illustrate the relationship between costs and measures of effect of interest. For the cost per QALY analyses cost-effectiveness acceptability curves (CEAC) will be presented. Deterministic sensitivity analysis will be conducted to explore sources of uncertainty.

21.2. Model-based economic evaluation

The 12-month follow-up of the trial will not capture all the costs and health outcomes associated with the interventions, as some events will be incurred over a longer timeframe. Therefore, an economic decision model will be developed to extrapolate costs and outcomes over the lifetime of the child and to compare hypothetical variations of the intervention that differ according to the component delivered. We anticipate the model will be a microsimulation model. We will work with our PPI and clinical team to design a model reflecting the child's journey both with and without the intervention. The model will be constructed following guidelines for best practice in economics modelling.⁵¹ The use of services both with and without the intervention will be modelled using data obtained from the trial and longer-term follow-up. Further data will be systematically derived from the literature and from expert clinical input (e.g. the Centre for the Evaluation of Value and Risk in Health (CEVR) Cost Effectiveness Analysis (CEA) Registry).

The model will be used to produce estimates of costs and QALYs (from the CHU9D and SF-6D). Further data for the economic model (for instance predicted uptake rates for alternative configurations of the intervention) will come for the DCE (please see Section 21.3 for more details). Relative efficiency will be reported in the same way as for the within trial analysis. The model will be probabilistic, with appropriate distributions used for the various parameters. The choice of which distributions will depend upon the data available and recommendations for good practice in modelling. The results will be presented as point estimates of costs, QALYs, incremental costs, QALYS, CCA outcomes and estimates of incremental cost per QALY gained. They will also be presented as plots of costs and effects and cost-effectiveness acceptability curves. The model will be developed in a suitable software package (e.g. R).

21.3. Discrete Choice Experiment (DCE)

Discrete choice experiment (DCE) is a quantitative method increasingly used to elicit preferences from participants (e.g., patients, the public and policymakers). In a DCE, participants are presented with a series of alternative hypothetical options (e.g., different configurations of a service or intervention) described by a set of different attributes (e.g., how often the intervention is administered, which healthcare professionals are involved), with each attribute taking one of several levels (e.g., setting the intervention frequency at weekly, monthly or annually; varying whether the intervention involves consultant and/or wider allied healthcare professionals). Participants are asked to state their preferred choice between two or three competing options, each choice consisting of a combination of these attributes/levels.

In this study, a DCE will be developed utilising the findings from the embedded process evaluation qualitative interviews, and existing and ongoing PPIE inputs. As a distinct part of the process evaluation, we will carry out separate interviews (n=10) with parents/carers to identify the various attributes of the intervention(s) which impact patient/carer satisfaction, uptake, compliance, and adherence. Participants from the main trial will be identified through the process evaluation and PPIE groups, and a patient information sheet for the DCE qualitative interviews will be sent to prospective interviewees to enable informed consent. Interviews (approx. 30 mins) will be carried out in person, online or by phone, depending on the preferences of interviewees. The interviews will, with consent, be audio recorded, transcribed verbatim and edited to ensure anonymity of responses (all data collection, data handling and ethical procedures will be in-line with the process evaluation approach in 17.5-10).

A prototype DCE will be designed and trialled with a test group of service users (n=10) and PPIE advisors. This piloting work will help ensure participants' understanding of choice contexts, generation and testing of appropriateness and understanding of attributes/levels, task complexity, length, timing, and likely response rates, and whether participants are willing to trade between the different attributes pertaining to specific policies in the subsequent DCEs. If required, translations for the DCE will also be tested at this stage, to ensure comparable understanding between different language formats. The trial will also be used to determine whether data collection is possible via a remote questionnaire or whether data collection through phone interviews will be required. Throughout this process we will engage with our PPIE representatives to seek their thoughts on developing the testing materials for use in the pilot studies. Feedback will also be sought from patient facing staff members to determine if the DCE attributes/levels are in-line with their experience of service user expressed preferences and the realistic bounds of such services.

The final DCE will be administered through 25% (n=10) of cluster settings, with the aim to recruit 50:50 from CHESS and Usual Care clusters. If possible, settings will be chosen to represent a range of geographic/ethnic/socioeconomic populations (in-line with the process evaluation approach, section 17), as well as cluster caseload sizes. Intervention clusters will be taken from a subset of those recruited for process evaluation; requirement for control clusters will depend on data collection format (with preferred collection method of remote questionnaire not requiring cluster recruitment). The trial management team will support the identification of comparable matched control clusters to the intervention clusters used. Data will be collected at around month 9 of the data collection period. A patient information sheet will be included with the main data collection at 9 months to give more information about the purpose of the DCE. Although all included cluster participants will be asked to complete the DCE, due to the time required for completion it will be made clear that it is not part of the core data collection, and it is their choice to complete it. A completion rate of greater than 50% is anticipated (n>100) in each arm, with a total target sample size of n=240.

From the full DCE responses we will produce a ranked list of attributes and their relative importance to participants' intervention preferences, as well as trade-offs between attributes. Data will be analysed in a random utility framework using appropriate logistic regression methods such as conditional logit/multinomial logit models.

The DCE will also be used to predict uptake rates for alternative configurations of the intervention that differ according to the components delivered. These alternative configurations will be incorporated as additional comparators within the economic model, with costs and impacts assigned accordingly. This will allow the estimation of the relative efficiency of alternative configurations of the intervention to inform decisions about whether the intervention could be tailored.

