9.3. Simple random sampling

Simple random sampling will be the standard method used to randomly select which children and their parent to invite to participate in the data collection for the trial. We will also evaluate targeted sampling based on socioeconomic status in a Study Within A Trial (SWAT); see section 22.2. The cluster PI, or their delegate, will send the full, non-identifiable caseload list of potential participants to CHaRT at the central trial office in an excel file format (or similar) using a secure file transfer system (such as a password protected encrypted file/ZendTo). This list will consist of a non-identifiable ID and a postcode for the child. The trial statistician will import the tables to STATA v18 for simple random sampling. Appropriate tools will be used to obtain deprivation data for the postcodes provided by the sites. Each eligible child will then be allocated a random number (using runiform() in STATA). A table which includes unique code, postcode, index of multiple deprivation(IMD) and assigned random numbers which has been generated will be exported into excel file and a process verification check will be conducted to ensure no duplicates or errors. The trial statistician will send the excel file back to the PI/delegate using a secure file transfer system (such as ZendTo). The PI/delegate will invite the parents of the sampled children to participate in data collection in CHESS, beginning with the randomly assigned first child on the list and continue through the list until the cluster target sample of 24 parents have agreed to participate in the data collection and follow up in CHESS, or the full list exhausted. The cluster PI will receive guidance from the research team as required.

Caseload and clinical lists are excluded from the sampling frame if they: involve very little contact with parents (e.g. services provided primarily to education settings); provide service to an organisation external to the approved trial organisation (e.g. a neighbouring NHS organisation); offer tertiary or other similar highly specialist care to a narrowly concentrated group (e.g. a specialist Fragile X service). Any discussions and judgements about excluding parts of caseloads or lists will be recorded by the research team, and in the site file.

10. Informing parents and children within clusters

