15.3. Follow-up

The vast majority of the parent reported outcomes will be collected at baseline, 6, and 12 months post-randomisation, using questionnaires completed at home using their preferred method of completion (phone, post, email or in-person). The primary outcome measure (PEDI-CAT) uses computer adapted testing, which means it cannot be completed on paper. The questionnaires will include PEDI-CAT, SF-36v2, CHU9D, Vineland 3 Coping Skills Subdomain, and questions about current and recent treatment, satisfaction with treatment and harms. First reminders will be issued to participants (according to their stated contact preference). If there is no response, up to two follow-up reminders (according to their stated contact preference) will be attempted – with at least one of these via text message to allow for a change of postal / email address. Test-retest evaluation will require re-administration of the 12-month measurements 2 weeks after initial data collection, and will be collected from a 20% subset (Target Sample Size = 192, see section 22.5 for selection methods) of total participants. The Discrete Choice Experiment (DCE) and Time and Travel questionnaire (TTQ) will be collected at approximately 9 months post-randomisation only, with the DCE being completed by a sub-set of the respondents only (Target Sample Size = 240, see section 21.3 for selection methods).

Questionnaires will be administered to all parents consented for data collection, regardless of adherence with treatment, unless they have opted out of questionnaire follow-up. This means that consented parents and children who have not received their allocated treatment, have received the non-allocated treatment, or where therapy has been discontinued, will continue to be followed up in the study.

If questionnaires are returned as non-deliverable, attempts will be made by the local cluster team or staff at the Trial Office to trace the participant. In case of non-return of questionnaires, attempts are made by local cluster staff or staff at the Trial Office to trace the participant directly, and/or indirectly by contacting the GP.

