22.3. Health economics outcome measurement SWAT

While all the health measures we propose to use have been intensively tested and are widely used across populations (with some of the measures being evaluated in thousands of studies in different populations to date), evidence of their psychometric properties in the context of trials in the present population is limited. This specific SWAT will aid interpretation of the findings of this trial, but also support researchers in the design of future trials in this or similar participant groups.

As part of this SWAT, we will assess the basic measurement and psychometric properties of the health economic measures (CHU9D, SF-36, and ICECAP-CES) at 12-month follow-up; 12 month data will be used as baseline measures are taken prior to cluster randomisation. Assessment will include the percentage of completed measures with missing data; floor/ceiling effects; test-retest reliability; convergent/divergent validity; agreement and known-group validity

Test-retest evaluation will require re-administration of the 12-month measurements 2 weeks after initial data collection, and will be collected from a 20% subset (n= 192) of total participants. Similarly to the DCE (section 21.3) we will select a subset of intervention and control clusters to undertake test-retest measurements, these clusters will be separate to the DCE clusters to ensure participants are not unduly burdened with data collection.

Provisional measurements of percentage of completed measures with missing data will be evaluated following baseline and 6-month period of the pilot trial, to highlight any data collection issues, with full SWAT evaluation completed after 12-month data collection for the full trial.

Primary subgroups (control and intervention) and secondary subgroups (sex, mobility, and socioeconomic deprivation) will also be evaluated for percentage of completed measures with missing data, floor/ceiling effects and test-retest reliability.

We will pay specific attention to evaluation of the CHU9D, as work is ongoing in validating it for children in our target age group.

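### The discrete choice experiment's stated completer numbers do not follow from its design: ten clusters of 24 at 50% completion give about 60 per arm, and 240 is the number approached

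*Protocol*

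**What the plan says.** Section 21.3 sets the scale of the DCE: "The final DCE will be administered through 25% (n=10) of cluster settings", "with the aim to recruit 50:50 from CHESS and Usual Care clusters". Within those clusters nobody is pre-selected: "Although all included cluster participants will be asked to complete the DCE", completion is voluntary. The expected yield is then given as "A completion rate of greater than 50% is anticipated (n>100) in each arm, with a total target sample size of n=240".

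Section 15.3 describes the DCE as completed by only part of the respondents and gives the figure again: "Target Sample Size = 240, see section 21.3 for selection methods".

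Cluster size is fixed elsewhere. Section 18.1 says "each cluster will recruit 24 children, a total sample size of 960", and section 9.3 has the local investigator work down the sampled list "until the cluster target sample of 24 parents have agreed to participate in the data collection", or until the list runs out. So 24 is a ceiling for each cluster.

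**The concern.** The sentence in 21.3 joins three figures: a completion rate above 50%, more than 100 in each arm, and a total of 240. Given ten clusters of at most 24, they cannot all describe completed responses. The per-arm count is too high for the rate beside it, and the total leaves no room for anyone to decline, although the same paragraph says that completing the DCE is optional.

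What is at stake is limited. The DCE is to rank and trade off attributes and to predict uptake. Those predictions feed the economic model for alternative configurations of the intervention (21.2 and 21.3) and the budget impact analysis for the intervention as delivered (21.4). If the attributes, levels and choice sets are laid out for 240 completers, or for more than 100 per arm, while the stated floor yields 120, the design may ask more of the data than they can bear. No part of the primary outcome or of the main sample size depends on this.

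**Working it through.** **Inputs**
- Clusters in the trial: 40; clusters giving the DCE: 25%, i.e. 10 (21.3).
- Split: 50:50 by arm (21.3), taken as 5 clusters per arm.
- Parents per cluster: 24, as a maximum (18.1, 9.3).
- Completion: above 50%, so 50% is the floor (21.3).
- Drop-out of about 15% (18.1): used below only as a sensitivity assumption, because 21.3 does not apply it to the DCE.

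**Step 1. Reproduce 240.** Approached = clusters × parents per cluster = 10 × 24 = 240, which is also 0.25 × 960. The figure reproduces exactly, as a count of everyone in the ten clusters before any non-response.

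**Step 2. Try to reproduce n>100 in each arm.** Approached per arm = 240 / 2 = 120. Completers per arm = 120 × completion rate.

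| Completion | Per arm | Total |
|---|---|---|
| 50% | 60 | 120 |
| 60% | 72 | 144 |
| 70% | 84 | 168 |
| 80% | 96 | 192 |
| 90% | 108 | 216 |
| 100% | 120 | 240 |

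At 50% the result is 60, so the stated figure is not reproduced.

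**Step 3. Completion needed for the stated figures.** For 100 per arm: 100 / 120 = 83.3%; the first whole number above 100 is 101 / 120 = 84.2%. For 240 completers: 240 / 240 = 100%. An unequal split does not help, because more than 100 in both arms means more than 200 in total, and 200 / 240 is again 83.3%.

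**Step 4. Other readings**
- n>100 over both arms together: 240 × 0.50 = 120. This fits.
- The same with 15% already lost (assumption): 240 × 0.85 = 204, and 204 × 0.50 = 102, or 51 per arm. The total still exceeds 100; the per-arm figure does not. Over 100 per arm would then need 100 / 102 = 98%.
- Twenty per cluster, the size used in the power calculation: 10 × 20 = 200, 100 per arm, 50 completers per arm at 50%. This does not fit.

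Only the reading over both arms agrees with the 50% floor, with or without drop-out.

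**The case against.** **The rate is only a floor.** Completion could exceed 83%. That is true, and for this reason 60 per arm is a minimum under the protocol's own assumption and not a forecast. But the protocol offers n>100 as the count that goes with a rate above 50%, and it does not follow from that rate.

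**It is a misplaced phrase.** The words about each arm may belong to the completion rate, with n>100 as the overall count and 240 as the number approached. This is the most likely explanation. It makes the point one of labelling and not of a failed design, but the text as printed says otherwise in 21.3, and 15.3 reinforces it.

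**Controls may come from elsewhere.** Section 21.3 says that a remote questionnaire would not require control clusters to be recruited. No larger control number is given, however, and the CHESS arm would still hold 5 × 24 = 120 at most, so 60 at 50%.

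**The figures are provisional.** Section 21.3 pilots response rates and collection mode, section 21 leaves full detail to the health economics analysis plan, and the planned analysis uses all DCE responses with no stated comparison by arm. All of this stands and lowers the stakes. It does not make the printed numbers agree.

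**Stronger readings that the protocol does not support**
- A reader might infer the same fault in the test-retest sample, which "will be collected from a 20% subset (n= 192) of total participants". Here 0.20 × 960 = 192 is correct. Section 22.3 fixes neither the number of clusters nor a completion rate, so nothing conflicts.
- A reader might turn the shortfall into a loss of precision. The protocol sets no precision target for the DCE, and precision also depends on the number of choice tasks and the design, so no such ratio can be derived.
- A reader might conclude that more clusters are needed. CHESS-arm DCE clusters must come from those in the process evaluation, which number 6–8 plus 3–4, i.e. 9–12 (17.3), and these span both arms (17.4). The numbers can be put right without widening.

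**Conclusion.** The point holds as an internal inconsistency in sections 21.3 and 15.3. Ten clusters of 24 give 240 approached and 120 per arm. At the stated floor, that is about 60 completers per arm and 120 in total, against a printed figure of more than 100 per arm and a target of 240. The printed figures need completion above 83% and of 100% respectively.

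The result rests on full recruitment of 24 in each DCE cluster and on completion at the 50% floor; higher completion would raise it. The lower values of 51 per arm and 102 in total rest on a further assumption, that the trial's 15% drop-out has already occurred. That figure was set for the main sample size, whereas the DCE is given at about 9 months, and the 50% may already allow for lost families.

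This should be corrected before the choice design is settled. It does not touch the trial's primary conclusion.

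**What to change.** In sections 15.3 and 21.3:

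1. Label 240 as the number approached (10 clusters of 24, 120 per arm).
2. State the expected completers separately: at least about 60 per arm and 120 in total at 50%. If drop-out is to be allowed for, add about 51 and 102, marked as assuming 15% already lost.
3. Correct n>100 so that it refers to the total over both arms.
4. Size the choice design (attributes, levels and choice sets) to the expected completers and not to 240.

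If more than 100 completers in each arm was truly intended, the protocol should instead state and justify the completion rate above 83% that this requires.

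The change is to wording only. It needs no extra clusters, recruitment or parent burden. The one practical task is to check any draft choice design against roughly 100 to 120 completers.
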